5.0 PRIMARY OUTCOMES

- 5.1 Foley's catheter insertion to delivery interval
- 5.2 Maternal satisfaction with the labour induction process

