2.0 OBJECTIVE OF THE STUDY

The purpose of the study is to evaluate whether removal of foley's catheter after 6 hours compared to 12hours in multiparous women undergoing induction of labour will result in a shorter duration of intervention to delivery time and increase maternal satisfaction with the induction process.

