After catheter insertion, the patient will be monitored in the ward or labour suite with the cardiotocogram which is discontinued when reassuring. Standard care for Foley IOL in our centre is applied to both arms. They are allowed to ambulate. Analgesia is given upon request. Subsequent cardiotocogram is performed as indicated. Patients are transferred to labour and delivery suite if the catheter is spontaneously expelled before the designated 6 or 12 hours. The catheter is removed if spontaneous rupture of membrane occurs or there is clinical need as decided at the discretion of the care provider.

Upon Foley removal (or if spontaneously expelled before removal), a second Bishop score is recorded, artificial rupture of membranes performed, and oxytocin infusion is initiated according to standard IOL protocol (10 international units of oxytocin in 500mls of Hartmann solution, started at 6ml/hr [2 mU/min] and doubled every 30 minutes until 3–5/10 min regular painful contractions is achieved at which rate infusion rate is maintained to delivery if no untoward reaction, maximum dose at 96ml/hr [32 mU/min]). If artificial rupture of membranes is not possible or safe (i.e., fetal head at high station), oxytocin can be initiated prior to artificial rupture of membrane.

Failed ripening is diagnosed if Bishop score is ≤ 5 after removal of catheter. Patient will then be assessed and counselled by the care provider as standard care in these circumstances for medical induction with prostaglandin, oxytocin, another Foley or caesarean section. Standard care will be provided to all participants during their labour induction, intrapartum and postpartum. Care providers always have full discretion in deciding care to the participants' best interest.

Maternal satisfaction with the induction process will be assessed as soon as possible after delivery using the Visual Numerical Rating Scale scored from 0-10.

All date captured will be transcribed onto the Case Report Form.

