4.5 SAMPLE SIZE CALCULATION

To calculate our sample size for the primary outcome, we obtained data from literature review on:

Primary outcome 1: Induction to delivery interval

Bleicher et al reported mean induction to delivery interval in the multiparous subgroup for 6 hours vs 12 hours double balloon placement as 18.0 hours with SD 6.8 vs 22.6 hours SD 8.2, p= 0.04 respectively, a mean reduction of 4.6 hours in favour of 6-hour placement.(14)

Using https://www.openepi.com/SampleSize/SSMean.htm and applying alpha of 0.02 (Bonferroni correction for 2 primary outcomes), t test, 80% power, 1 to 1 ratio, 18.0 hours with SD 6.8 vs 22.6 hours SD 8.2, 54 women are required per arm (total 104). Factoring in the possibility of non-normal data distribution requiring Mann Whitney U test application, we increase sample size by 15% and assuming 10% dropout, we plan to recruit $54 \times 1.15/0.9 = 69$ in each arm (N = 138 women)

For maternal satisfaction, assuming a 1-point difference in the 11-point 0-10 visual numerical rating scale (VNRS) to be clinically relevant. Using https://www.openepi.com/SampleSize/SSMean.htm and applying alpha of 0.02 (Bonferroni correction for 2 primary outcomes), t test, 80% power, VNRS standard deviation of 2 for both arms, 81 women are required per arm (total 162). Factoring in the Mann Whitney U test application as satisfaction score is ordinal, we increase sample size by 15% and assuming 10% dropout, we plan to recruit $81 \times 1.15/0.9 = 103.5$ in each arm (total of 207 women). We rounded the required sample size of participants up to N = 210 in total to adequately cover for both primary outcomes.

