6.0 SECONDARY OUTCOMES

based on core outcome set for trials on induction of labour: CROWN

Maternal outcomes

Change in bishop score after intervention

Use of additional method for cervical ripening

Time to delivery after Foley's catheter removal

Mode of delivery

- a) spontaneous vaginal
- b) vacuum
- c) forceps
- d) caesarean section

Indication for caesarean section

Duration of oxytocin infusion

Maternal satisfaction-based allocation to intervention until birth (11-point VNRS)

Blood loss during delivery

Third -or fourth-degree tear

Maternal infection

Use of regional analgesia in labour?

Length of hospital stay

ICU admission

Cardiorespiratory arrest

[figure not shown]
Hysterectomy

Apgar score at 1	L and 5 minutes				
NICU admission	ı				
Cord pH					
Neonatal sepsis					
Birth weight					
Birth trauma					
Hypoxic ischaer	nic encephalopath	ny/need for ther	apeutic hypothe	ermia	

Trial Protocol

Patient admitted to antenatal ward or labor ward.

PROTOCOL FLOW CHART

CASE REPORT F	CASE REPORT FORM				
	ment: / / _ (dd/ mm/ yy)				TUDY NUMBER
EDD://	(dd/ mm/ yy)				
Patient charact				PATIE	NT STICKER
Gravida:	Para: Abo	ortion:			
Gestational age	e:				
Latest recorded	d Weight:	kg			
Height:	cm				
Education level	l:				
Up to prim	ary				
Secondary					
Diploma					
Degree					
Masters					
PhD					
Occupation:					
Employed					
Self emplo	yed				
Student					
Housewife					
Other:					
Ethnicity:					
Malay					
Chinese					
Indian					
Other:					
Indication/s for	· IOL:	 			
Pre induction B	ishop Score:				
Score	0	1	2	3	
Dilatation	Closed	1-2 cm	3-4	5 cm	
Length	> 4 cm	3-4 cm	1-2 cm	0	
Consistency	Firm	medium	soft	-	

mid

-2

anterior

-1 to 0

+1, +2

≤ -3

Posterior

Position

Station

Primary Outcomes:

1. IOL to delivery interval [Date/Time delivery - Date/Time catheter inserted

[figure not shown]
2. Maternal satisfaction

Rate your satisfaction with the experience of your allocated intervention of placement (of 6 or 12 hours) of the Foley catheter for labour induction.

Circle your score below (higher score, greater satisfaction)

0	1	2	3	4	5	6	7	8	9	10

10-totally satisfied

To be assessed as soon as possible after delivery (in all cases before hospital discharge)

Dates and times

1.	Date / Time catheter inserted: / / (dd/ mm/ yy):: (hr:min)
2.	Date / Time catheter removed/ dislodged: / / (dd/ mm/ yy):: (hr:min)
3.	Date / Time ARM/SROM: / / (dd/ mm/ yy):: (hr:min)

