Totally dissatisfied (To be assessed within 24 hours of delivery)

Totally satisfied

- 2) I would recommend my allocated intervention of placement (of 6 or 12 hours) of the Foley catheter for labour induction to a friend
 - a) Strongly agree
 - b) Agree
 - c) Neither agree nor disagree
 - d) Disagree
 - e) Strongly disagree

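### Co-primary outcome 2 is defined as satisfaction with labour induction, but the only 0-10 item asks about the allocated 6- or 12-hour catheter placement, which is narrower

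*Protocol*

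**What the plan says.** **Definition.** Section 5.0 gives the second primary outcome as "Maternal satisfaction with the labour induction process". The objective in Section 2.0 is to "increase maternal satisfaction with the induction process", and the aim at the end of Section 1.0 has the same object. Section 4.4 states: "Maternal satisfaction with the induction process will be assessed as soon as possible after delivery using the Visual Numerical Rating Scale scored from 0-10". The hypothesis in Section 3.0 speaks of maternal satisfaction without saying with what.

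**Measurement.** On the Case Report Form, item 2 under the primary outcomes reads: "Rate your satisfaction with the experience of your allocated intervention of placement (of 6 or 12 hours) of the Foley catheter for labour induction". It is scored 0 to 10. The page completed by the participant repeats this wording. The only other item she rates is a five-point agreement statement: "I would recommend my allocated intervention of placement (of 6 or 12 hours) of the Foley catheter for labour induction to a friend".

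**Secondary list.** Section 6.0 includes "Maternal satisfaction-based allocation to intervention until birth (11-point VNRS", and the form has no separate question for it.

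**Sample size.** Section 4.5 plans for satisfaction by "assuming a 1-point difference in the 11-point 0-10 visual numerical rating scale (VNRS) to be clinically relevant", with SD 2, alpha 0.02 and 80% power.

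**The concern.** The outcome is defined on one construct and scored on another. Section 4.4 describes an induction that continues after the catheter is out: a second Bishop score, membrane rupture, oxytocin and, if ripening fails, further methods. The scored item directs the woman to one part of this, the catheter placement she was allocated, and names its duration.

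That duration is what randomisation changes, and the trial cannot be blinded. The 6-hour arm could score higher because the device came out sooner, even if the rest of the induction was experienced no better. Followed as written, the plan would report such a result as greater satisfaction with induction, which the item does not establish.

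The Section 6.0 line adds a second ambiguity. A satisfaction score covering allocation to birth spans a different period from catheter placement. If it is a separate outcome, nothing on the form collects it. If it is the same score, one variable is listed as both primary and secondary.

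**Working it through.** This is mainly a comparison of texts. The arithmetic only shows how much rests on the outcome.

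**Wording side by side**

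1. Object of the rating in Sections 1.0 (aim), 2.0, 4.4 and 5.2: the induction process.
2. Object of the rating in the 0-10 item, printed twice on the form: the experience of the allocated catheter placement, with 6 and 12 hours named.
3. Object of the five-point recommendation item: again the allocated placement, so it does not fill the gap.
4. Object of the Section 6.0 line: a period ending at birth, on an 11-point scale, with no item attached.

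No item on the form as shown has the object in line 1.

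**Can the two constructs diverge?** The Protocol's own outcome list implies that they can. Additional ripening, oxytocin duration, time from catheter removal to delivery and mode of delivery are separate secondary outcomes. Any of them could differ between arms independently of how long the catheter was in place.

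**What rests on the outcome (Section 4.5)**

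- Inputs: difference 1, SD 2 in both arms, two-sided alpha 0.02, power 80%. The Protocol does not state sidedness; two-sided reproduces its figure.
- Formula: n per arm = 2 × SD² × (z for 1 − alpha/2 + z for power)² / difference².
- Numbers: 2 × 4 × (2.326 + 0.842)² / 1 = 8 × 10.04 = 80.3, so 81 per arm, as stated.
- Inflation: 81 × 1.15 / 0.9 = 103.5 per arm, 207 in total, rounded to 210, as stated.
- Interval outcome: 54 × 1.15 / 0.9 = 69 per arm, 138 in total, as stated.
- Difference: 210 − 138 = 72 women beyond what the interval outcome requires.

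The calculation is sound on its inputs. Aligning the wording leaves it unchanged unless the SD of 2 or the 1-point difference is revised. The Protocol gives no source tying either value to one construct rather than the other.

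**The case against.** The best defence is that the item is a reasonable, if loosely worded, way of scoring the stated outcome. The form prints it as the primary outcome, it mentions labour induction, and it is asked after delivery, when the woman has been through everything. It does not tell her to exclude oxytocin or membrane rupture, and under Section 4.4 those steps follow on catheter removal, so their timing is part of what allocation changes. **This stands in part.** A reader might infer that the trial does not measure its primary outcome at all. The documents do not support that: the item is a narrower and ambiguous version of the outcome, not an unrelated one.

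A reader might also infer that naming the durations biases the score by some definite amount. The documents give no basis for a figure. Women know their allocation whatever the form says, so removing the durations would not remove the effect of an unblinded rating.

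The 72 additional women show that satisfaction drives the trial size. They do not measure harm from the wording, and they also add power for the interval outcome.

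A longer or more interventional induction would still be visible in the interval co-primary and in the secondary outcomes. That limits how far a favourable score could mislead. It does not make the score a measure of what Section 5.2 names.

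Finally, the Section 6.0 line is ungrammatical and may only be a redundant listing of the same score. That is plausible, but the Protocol does not say so.

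**Conclusion.** The mismatch is real and should be resolved, because it concerns a co-primary outcome and the one that sets N = 210. The definition refers to the induction process. The only 0-10 satisfaction item refers to the allocated catheter placement, which is narrower and is the feature that separates the arms. A result on that item supports a conclusion about satisfaction with the placement; by itself it does not support one about induction. The Section 6.0 score is either uncollected or a duplicate.

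The effect on the result cannot be sized from the Protocol. The conclusion rests on reading the printed item as the one that supplies the primary outcome, as the form labels it, and on there being no other satisfaction item than those shown. A later analysis plan could not repair the gap, since it cannot recover a question that was not asked. The sample size arithmetic is not in question.

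**What to change.** Make the definition and the item agree; which one changes depends on whether scores have been collected.

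- **Before any woman has been rated:** reword the 0-10 item, in both places on the form, so that it asks about the construct named in Section 5.2 and does not mention 6 or 12 hours.
- **If women have already been rated:** keep the item. Restate the aim in Section 1.0, Sections 2.0, 3.0, 4.4 and 5.2, and the planned conclusion as satisfaction with the allocated catheter placement.
- **In either case:** delete the Section 6.0 satisfaction line, state that it is the same measure as the primary, or give it an item of its own.

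The cost is one item or one definition, plus one line in Section 6.0, with no additional visit and no change to the sample size calculation. The main downside is timing: changing the item after recruitment has begun would split a co-primary outcome across two questions. Restating the outcome instead avoids this, at the price of a narrower claim.

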6.0 SECONDARY OUTCOMES

based on core outcome set for trials on induction of labour: CROWN

Maternal outcomes

Change in bishop score after intervention

Use of additional method for cervical ripening

Time to delivery after Foley's catheter removal

Mode of delivery

- a) spontaneous vaginal
- b) vacuum
- c) forceps
- d) caesarean section

Indication for caesarean section

Duration of oxytocin infusion

Maternal satisfaction-based allocation to intervention until birth (11-point VNRS)

Blood loss during delivery

Third -or fourth-degree tear

Maternal infection

Use of regional analgesia in labour?

Length of hospital stay

ICU admission

Cardiorespiratory arrest

[figure not shown]
Hysterectomy

Apgar score at 1	L and 5 minutes				
NICU admission	ı				
Cord pH					
Neonatal sepsis					
Birth weight					
Birth trauma					
Hypoxic ischaer	nic encephalopath	ny/need for ther	apeutic hypothe	ermia	

Trial Protocol

Patient admitted to antenatal ward or labor ward.

PROTOCOL FLOW CHART

CASE REPORT F	CASE REPORT FORM				
	ment: / / _ (dd/ mm/ yy)				TUDY NUMBER
EDD://	(dd/ mm/ yy)				
Patient charact				PATIE	NT STICKER
Gravida:	Para: Abo	ortion:			
Gestational age	e:				
Latest recorded	d Weight:	kg			
Height:	cm				
Education level	l:				
Up to prim	ary				
Secondary					
Diploma					
Degree					
Masters					
PhD					
Occupation:					
Employed					
Self emplo	yed				
Student					
Housewife					
Other:					
Ethnicity:					
Malay					
Chinese					
Indian					
Other:					
Indication/s for	· IOL:	 			
Pre induction B	ishop Score:				
Score	0	1	2	3	
Dilatation	Closed	1-2 cm	3-4	5 cm	
Length	> 4 cm	3-4 cm	1-2 cm	0	
Consistency	Firm	medium	soft	-	

mid

-2

anterior

-1 to 0

+1, +2

≤ -3

Posterior

Position

Station

Primary Outcomes:

1. IOL to delivery interval [Date/Time delivery - Date/Time catheter inserted

[figure not shown]
2. Maternal satisfaction

Rate your satisfaction with the experience of your allocated intervention of placement (of 6 or 12 hours) of the Foley catheter for labour induction.

Circle your score below (higher score, greater satisfaction)

0	1	2	3	4	5	6	7	8	9	10

10-totally satisfied

To be assessed as soon as possible after delivery (in all cases before hospital discharge)

Dates and times

1.	Date / Time catheter inserted: / / (dd/ mm/ yy):: (hr:min)
2.	Date / Time catheter removed/ dislodged: / / (dd/ mm/ yy):: (hr:min)
3.	Date / Time ARM/SROM: / / (dd/ mm/ yy):: (hr:min)
4.	Date / Time oxytocin infusion start (if any):/ (dd/ mm/ yy):: (hr:min)
5.	Date / Time oxytocin infusion stop (if before delivery):
	// (dd/ mm/ yy):: (hr:min) @ delivery
6.	Date / Time of 2nd stage: / / (dd/ mm/ yy):: (hr:min)
7.	Date / Time of pushing:/ / (dd/ mm/ yy):: (hr:min)
8.	Date / Time of delivery: / / (dd/ mm/ yy):: (hr:min)
9.	Date / Time of Hospital Discharge (as per EMR):/ (dd/ mm/ yy)::(hr:min)

Secondary Outcomes

Maternal Outcome

1. Bishop score at catheter removal/ dislodgement

Score	0	1	2	3
Dilatation	Closed	1-2 cm	3-4 cm	5 cm
Length	> 4 cm	3-4 cm	1-2 cm	0
Consistency	Firm	medium	soft	
Position	Posterior	midline	anterior	
Station	-3	-2	-1 to 0	+1, +2

"	acion					1 10 0	. 1,	. 2		
2.	Addition	Additional cervical ripening used?								
	a)	Fole								
	b)		, taglandin Please :	specify:						
	c)									
	d)	c) Others Please specify:								
3.	Mode of	Delive	ry:							
	a)	SVD								
	b)	Caes	arean section. In	dication:						
	c)	Instr	umental delivery	. Indication	:					
		i. Fo	rceps							
		ii. Va	cuum							
4.	Use of a	nalgesi	a in labor?							
	Circle as many as used									
	a)	a) None								
	b)	Entonox								
	c)	Opia	te i.m							
	d)	Neuraxial analgesia								
	e)	e) Others. Please specify								
5.	Estimated blood loss at delivery: ml									
6.	Type of p	perinea	al tear sustained:							
	Intact perineum/ First°/ Second°/ Third°/ Fourth°/ Episiotomy									

7.	Required ICU admission
	Yes
	No
	Reason for admission:
8.	Cardiopulmonary resuscitation (CPR) before hospital discharge
	Yes
	No
9.	Hysterectomy before hospital discharge
	Yes
	No
10	Maternal fever (highest recorded temperature from IOL to discharge): ⁰ C
10.	whatemarrever (highest recorded temperature from 102 to discharge).
11.	Antibiotics given (from IOL to discharge)
	Yes Indication
	No

1.	Apgar Score: 1 mins / 5 mins
2.	Cord Arterial pH: Base excess :
3.	Birth weight: kg
4.	Required neonatal admission: Yes No Place of admission: PNW / SCN / NICU / Others Indication for admission:
5.	Diagnosed with Hypoxic ischaemic encephalopathy (HIE) Yes No
6.	Cooling therapy for HIE Yes No
7.	Neonatal sepsis diagnosed Yes Please specify
8.	Birth trauma Yes Please specify No

Neonatal outcome

To be completed by participant

 Rate your satisfaction with the experience of your allocated intervention of placement (of 6 or 12 hours) of the Foley catheter for labour induction.
 Circle your score below (higher score, greater satisfaction)

0	1	2	3	4	5	6	7	8	9	10

Totally dissatisfied (To be assessed within 24 hours of delivery)

Totally satisfied

- 2) I would recommend my allocated intervention of placement (of 6 or 12 hours) of the Foley catheter for labour induction to a friend
 - a) Strongly agree
 - b) Agree
 - c) Neither agree nor disagree
 - d) Disagree
 - e) Strongly disagree

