4.3 POPULATION OF STUDY

Multiparous women planned for elective induction of labour for various indications admitted will be assessed for enrolment using the Eligibility Form.

Eligibility form

Inclusion Criteria

•	Multiparous women (at least 1 vaginal delivery ≥ 24 weeks)	
•	Age ≥ 18 years	
•	Gestational age of ≥ 37 weeks	
•	Singleton pregnancy	
•	Cephalic presentation	
•	Intact membrane	
•	Reassuring fetal heart tracing	
•	Absence of significant contraction ≥ 2 in 10 minutes	
•	Successful Foley insertion for IOL	
•	Bishop score ≤ 5	

Exclusion Criteria

•	History of caesarean delivery or hysterotomy/ uterine	
	perforation/ previous myomectomy	
•	Latex Allergy	
•	Estimated Fetal weight less than 2kg or > 4kg	
•	Known major fetal malformations	
•	Contraindication for vaginal delivery	
•	Patient who is suspected COVID 19 infection or COVID 19 positive	

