4.4 METHODS

This is a randomised control trial involving multiparas at term (≥ 37 weeks) who are planned for IOL for various indications. Participant information sheet with be given to all potential recruits and any inquiries by the participants will be answered by the recruiting care provider. Written consent will be obtained from all participants.

All participants will undergo standard assessment by the care provider before their IOL; including their personal characteristics, obstetric assessment and fetal wellbeing (using a nonstress cardiotocogram) assessment.

Insertion of Foley Catheter

Participants will be positioned in the dorsal position. Bishop score will be ascertained during the vaginal examination prior to Foley insertion. A Foley catheter size 16F is then introduced through

the external os using either by digital or speculum method (at discretion of introducer). Once the tip of the catheter has passed the internal os by 4 to 5cm, the balloon will be inflated with 80ml of water and retracted so the balloon rests on the internal cervical os. The other end of the Foley catheter will be taped without tension to the medial aspect of the women's thigh. (19)

Randomisation

Randomisation will be performed and intention to treat revealed only after successful Foley insertion. Randomisation is done by opening the lowest number, sealed and opaque envelope that is available, assigned in strict order. Randomisation sequence will be generated using a random number generator at Random.org in random blocks of 4 or 8 sequence, generated by an investigator who is not involved in recruitment. Blinding is not possible due to the nature of the intervention.

Participants will be randomised into two trial arms: Foley removal following its insertion

1. at 6 hours

or

2. 12 hours

Trial will be closely monitored by the supervisors. Any serious adverse effects (SAE) will be reported to UMMC-MREC committee for discussion and review of the clinical trial.

Labour Induction Care

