6.1 STATISTICAL ANALYSIS

Data will be entered into SPSS statistical software. Normally distributed continuous data will be analysed with paired Student's t test. Chi square test will be used for categorical or nominal data and Mann- Whitney U test will be used on non-normally distributed or ordinal data.

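### Minor: the planned comparison of raw change in Bishop score leaves out an adjustment for the pre-insertion score that is never materially less precise and needs no new data

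*Protocol*

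**What the plan says.** Protocol section 6.0 lists "Change in bishop score after intervention" among the maternal secondary outcomes. In the case report form, item 1 under the maternal secondary outcomes is the second score itself: "Bishop score at catheter removal/ dislodgement".

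Section 4.4 fixes the timing. "Bishop score will be ascertained during the vaginal examination prior to Foley insertion", and "Randomisation will be performed and intention to treat revealed only after successful Foley insertion". At removal or expulsion "a second Bishop score is recorded". Section 4.3 requires "Bishop score ≤ 5" at entry.

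Section 6.1 names a chi-square test for categorical data and two tests for scores: "Normally distributed continuous data will be analysed with paired Student's t test", and "Mann- Whitney U test will be used on non-normally distributed or ordinal data". No covariate is mentioned anywhere in the protocol. It gives no SD, correlation, target difference or power for the Bishop score.

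**The concern.** Sections 6.0 and 6.1 together yield an unadjusted comparison of second minus first score. Subtracting the first score in full is the best use of it only if, within an arm, each extra point at baseline carries through as a full extra point at removal. If less carries through, the subtraction over-corrects. It then leaves avoidable baseline variation in the outcome and lets a chance baseline difference between arms move the estimate.

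What is at stake is limited but real. Reduced ripening is a plausible price of shorter placement, and section 4.4 makes the second score consequential by using it to diagnose failed ripening. A noisier comparison makes a true loss of ripening at 6 hours somewhat harder to see. The baseline value needed to avoid this is already collected.

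**Working it through.** **The plan's own figures.** None exists for the Bishop score. The sample size in section 4.5 concerns the two primary outcomes and reproduces with n = (z₀.₉₉ + z₀.₈₀)² × (SD₁² + SD₂²)/difference², where (2.326 + 0.842)² = 10.04:

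- Interval: 10.04 × (6.8² + 8.2²)/4.6² = 10.04 × 113.48/21.16 = 53.8, so 54 per arm; 54 × 1.15/0.9 = 69.
- Satisfaction: 10.04 × (2² + 2²)/1² = 80.3, so 81 per arm; 81 × 1.15/0.9 = 103.5, or 207 in total, rounded up to 210.

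Nothing below alters these numbers.

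**Identity.** Let s0 and s1 be the within-arm SDs of the first and second score, r their within-arm correlation (taken as common to both arms), and slope = r·s1/s0.

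- Var(change) = s0² + s1² − 2·r·s0·s1
- Var(adjusted) = s1²(1 − r²)
- Difference = (s0 − r·s1)² = s0²(1 − slope)², which is never negative and is zero only at slope 1.

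The covariate costs one degree of freedom. With 10% dropout, 210 × 0.9 = 189 women, and the variance factor is about 1 + 1/185 = 1.005.

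**Range of the gain (s0/s1 and r are assumptions).** Adjusted variance divided by change-score variance:

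| s0/s1 | r = 0.1 | r = 0.3 | r = 0.5 |
|---|---|---|---|
| 0.3 | 0.96 | 1.00 | 0.95 |
| 0.5 | 0.86 | 0.96 | 1.00 |
| 0.75 | 0.70 | 0.82 | 0.92 |
| 1.0 | 0.55 | 0.65 | 0.75 |

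The gain in effective sample size therefore runs from nil (ratio 1.00) to about 80% (1/0.55 = 1.82).

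**One worked case (all inputs assumed).** Take s0 = 1.32, s1 = 1.80, r = 0.29, so slope = 0.29 × 1.80/1.32 = 0.40.

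- Var(change) = 1.742 + 3.240 − 1.378 = 3.604, SD 1.90.
- Var(adjusted) = 3.240 × (1 − 0.0841) = 2.967, SD 1.72. Ratio 3.604/2.967 = 1.21.
- For an assumed true difference of 0.7 points at two-sided 5%, normal approximation, 105 per arm: standard errors 0.262 and 0.238, power about 76% and 84%. After 10% dropout: about 72% and 80%.
- Chance imbalance: the SD of the baseline difference between arms is 1.32 × √(2/105) = 0.18. A 1-in-20 imbalance is 1.96 × 0.18, about 0.36 points, and moves the raw-change comparison by 0.36 × (1 − 0.40), about 0.2 points.

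**Simulation check (assumed inputs).** Integer scores, first score cut at 5, 95 per arm, true effect about 0.7 points, s0/s1 about 0.73 to 0.79, two-sided 5%:

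| Observed r | SE, change | SE, adjusted | Power, change | Power, adjusted | Power, Mann-Whitney on change |
|---|---|---|---|---|---|
| 0.14 | 0.337 | 0.290 | 54% | 66% | 52% |
| 0.30 | 0.314 | 0.283 | 64% | 72% | 63% |
| 0.47 | 0.255 | 0.239 | 76% | 82% | 76% |

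The direction agrees with the identity, and moving to the rank test on the change does not recover the loss.

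**The case against.** The strongest reply is that covariate adjustment of an unpowered secondary outcome is ordinary analysis-plan content, and that 6.0 names an outcome rather than a model. The second half is right: regressing the change on arm and first score gives exactly the same arm difference and standard error as regressing the second score on them. The outcome wording therefore does not force the inefficiency, and it could stay. The first half does not dispose of the point, because the protocol is not silent. Section 6.1 names the tests, and none uses a covariate.

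The score is also ordinal and bounded, and 6.1 sends ordinal data to Mann-Whitney. A linear model brings an assumption of its own, so a sensitivity analysis is needed. This does not favour raw change, since subtracting two scores already treats the points as equally spaced.

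Several stronger readings are tempting, and the document does not support them:

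- *The entry cap of 5 causes the loss.* With a linear relation the cap leaves the slope unchanged and shrinks s0, so it limits s0²(1 − slope)².
- *Change is the only ripening measure.* Section 6.0 also lists the need for a further ripening method, and the case report form lists the second score itself.
- *Change is noisier than the second score alone.* That holds only if r < s0/(2·s1).
- *The result would be biased.* Under randomisation a baseline imbalance is chance variation already reflected in the standard error.
- *A large loss of power is demonstrated.* Every power figure above rests on assumed inputs.

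For this outcome the word paired in 6.1 is the more serious fault: pairing first and second scores tests change within an arm and does not compare the arms. That is a separate correction.

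**Conclusion.** The concern holds as a minor, optional improvement. The protocol plans an unadjusted comparison of change although a valid pre-randomisation covariate is at hand. Adjustment is never less precise apart from one degree of freedom, and it removes the linear effect of a chance baseline imbalance. That conclusion follows from algebra and needs no outside figure, only a common within-arm slope.

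The size of the gain cannot be taken from the document. It is nil if the slope is 1 and about 80% in effective sample size at the far end of the assumed range (s0/s1 = 1.0, r = 0.1). The consequence is confined to the precision of one unpowered secondary outcome. The primary outcomes, the validity of the randomised comparison and N = 210 are untouched, and the stated hypotheses concern interval and satisfaction, not equal ripening.

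**What to change.** Add one sentence to section 6.1 and align the line in 6.0. The Bishop score at catheter removal or expulsion (or, equivalently, its change from the first score) is compared between arms by linear regression with the pre-induction Bishop score as covariate, reporting the adjusted difference with its 95% CI. Because the score is ordinal and bounded, name a proportional-odds model with the same covariate, or the planned Mann-Whitney test, as a sensitivity analysis. Raw change by arm may stay as a descriptive column.

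The cost is a sentence of text and one degree of freedom. It needs no new data, visits or participants.
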